A pilot single-blind two-arm parallel randomised control trial will be conducted in dental clinics in the Midlands, Southeast and Northwest England. A total of 34 adult patients, who require the extraction of a single-rooted tooth, will be randomly assigned to experimental and control group at a 1:1 ratio.

After tooth extraction, the bone substitute will be introduced into the socket; the control group A will receive the bovine-derived bone the intervention group B the bioactive glass derived bone. All patients will be reviewed after 2 weeks for suture removal. Patients' follow-up will be 24 weeks after the procedure. Outcome data will be collected at baseline and at 24 weeks. The primary outcome is the effectiveness of bioactive glass derived bone in preserving the alveolar ridge dimensions compared to bovine-derived bone. This will be assessed by measuring changes in the width of the alveolar ridge from baseline (augmentation) to 24-week post augmentation using a linear regression model including baseline measurements as covariates. Secondary outcomes are:

- Changes in the height of the alveolar ridge from augmentation to 24-week post augmentation
- Changes in vertical crestal bone level at 24-week post augmentation
- Presence of bone markers at 24-week post augmentation
- Qualitative Bone infiltration at 24-week post augmentation

Discussion

The results of this pilot study will inform the design and implementation of a full scale randomised controlled trial to investigate the effectiveness of bioactive glass derived bone compared with bovine derived bone in preserving the alveolar bone of a tooth after an extraction.

Ethics and dissemination

Ethics approval was obtained from the University of Central Lancashire xxxxxx. Results will be published in peer-review and professional journals, presented at scientific conferences, and disseminated to service users and their families via media.

Trial registration number: XXXXX

Effectiveness of two bone substitutes, natural and synthetic, in preserving the alveolar ridge of single-rooted teeth: a single-blind, parallel randomised controlled trial

Background

What is the problem to be addressed?

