It is a pilot single-blind two-arm parallel randomised control trial that aims to assess the differences between two bone substitutes, natural versus synthetic. The study will mimic the routine practice, and patients will be randomly allocated to receive either the natural (control) or synthetic (intervention) bone substitutes. The patient follow-up period will be 24 weeks from the baseline data collection point.

Methods

Study setting

The study will be conducted in dental clinics in the Midlands, Southeast England and Northwest England.

Eligibility criteria for participants

Inclusion criteria

Adult patients (age >18) in need of extraction of a single-rooted tooth attending the clinics selected for the study

Single units in a dentate patient

Non-surgical extraction – no flap raised, and no bone removed

Intact socket walls post-extraction

Bleeding sockets

Stable periodontal health

ASA Class I or II patients. The American Society of Anaesthesiologists (ASA) classification is a system of physical status evaluation developed to offer clinicians a simple categorisation of a patient's physiological status to help predict operative risks (Appendix 1).

Exclusion Criteria

Multiple adjacent extractions

Presence of active periodontal disease

Socket walls not intact - >50% bone loss in any of the four walls

Sclerotic sockets post-extraction – the socket does not fill up with blood post-extraction

Denture wearer – the extraction socket site under the load of a denture

Patients on medication that can affect bone healing e.g., bisphosphonates (oral or intravenous), selective serotonin reuptake inhibitors (SSRI), methotrexate, proton pump inhibitors (PPI)

Uncontrolled diabetes

Smokers

Immunosuppressed Patients

Patients with a history of myocardial Infarction in the last year

ASA Class > II patients (17)(Appendix 1)

Intervention

The test bone substitute is Bonalive[®], bioactive glass S53P4, which contains SiO₂, Na₂O, CaO, and P₂O₅ (granule size 0.5-0.8mm) (18) Bonalive[®] is osteoconductive, meaning that it has the ability of promoting bone growth across the granules and the grafting area and slowly replace it with new bone over time. Bonalive[®] is osteostimulative and has antibacterial properties (19).

Comparator

The comparator is Bio-Oss[®], deproteinized bovine bone granules (granule size 0.25- 1mm) (20). Bio-Oss[®] is osteoconductive, which means it acts as a scaffold only for new bone to grow (21,22).

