Both products have a low substitution rate and are expected to have similar ridge support and shape maintenance capability.

Management of the bone substitutes

The bone substitutes will be used according to the manufacturers' instructions and protocols (Appendix 2 and 3). The materials are supplied in sealed sterile packaging with clearly displayed expiry dates, LOT numbers and CE marks. The materials' LOT numbers and expiry dates will be recorded on the patient records and on a separate 'Surgery Logbook' with an identification number for the patient traceable to the appropriate batch of materials.

The use of the material will follow standard surgical protocols and excess material will be discarded according to clinical waste guidelines.

Clinical procedure

The bone substitute will be used according to the ridge preservation protocol, which will be standardised between the different centres. As part of standard clinical practice, a periapical radiograph will be taken before an extraction. Following the removal of a tooth, the inflamed area of the socket will be curetted to ensure a 'clean' socket. The case will be excluded if:

- The socket walls are very sclerotic with a lack of fresh bleeding, which is essential for healing.
- The socket walls are damaged. The limit is a loss of 50% or more of one of the walls. The assessment of the extraction socket will be done by the clinicians performing the procedures (23).

The bone substitute will then be introduced using a standard sterile protocol, with gentle packing of the material in the sockets to ensure the material reaches the apex of the socket but is not condensed with pressure. The socket will then be sealed with a collagen matrix with non-resorbable sutures. Review appointment for suture removal will be required 2 weeks post-procedure.

Patients will be advised not to fly for two weeks post-procedure or until after the clinicians have reviewed them. Intra-oral scans or impressions with clinical photographs will also be taken on the day the procedure is carried out. The follow-up will take place 24 weeks post-procedure, when a PA radiograph, intra-oral scans or impressions, clinical photographs and a minimally invasive trephine biopsy will be carried out.

Management of tissue samples in the dental clinic

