The procedure for processing the sample in the laboratory will be similar to that used in a study by Li et al. (25) Frozen tissue samples will be thawed in RNAlater®-ICE and lysed for RNA extraction using Qiagen RNeasy kit following the manufacturer's instructions. Following treatment with DNase-1 reagent and reverse-transcription of RNA samples using the SuperScript® VILOTM cDNA synthesis. SYBR green-based qPCR assays will be performed to analyse osteogenic gene expression, including Runx2, alkaline phosphatase, osteopontin and osteocalcin. The relative transcript levels of genes of interest will be analysed using the comparative CT (ΔΔCT) method. The range of relative transcript levels of the genes of interest will be presented as bar graphs, and statistical analysis will be performed at the level of ΔΔCT.

Table 1 Schedule of enrolment, intervention and assessments

	Study period				
	Enrolment	Allocation	Post-allocation		Close-out
Timepoint (weeks)	-W0	W0	W0	W2	W24
Enrolment					
Eligibility screen for patients	x				
Informed consent from patients	x				
List of other procedures	x				
Randomisation of patients		x			
Interventions					
Synthetic bone			x		
Natural bone			x		
Suture removal				x	
Assessments (Outcomes)					
Width			x		x
Height			x		x
Crestal bone					x
Histology					x
Bone Markers					x

Figure 1 CONSORT study flowchart

Criteria for discontinuing or modifying allocated interventions

- Participant withdraws consent
- The trial is discontinued
- Participant has an adverse reaction

The reasons for discontinuation will be documented (see Standard Operating Procedures).

Strategies for monitoring and improving protocol adherence

There are some measures that clinicians could adopt to improve patients' adherence to the research protocol, such as telephone calls, text reminders, and social support to educate patients. In addition, clinicians will have to create a welcoming, non-judgmental and accepting environment; educate patients about their role as research participants; establish a routine while maintaining flexibility; provide incentives for participation, parking spaces, and videoconferences.

Outcomes

Primary outcome

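### Does excluding cases at the post-extraction socket check break the intention-to-treat set?

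*Combined protocol and SAP*

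**What the plan says.** Eligibility depends partly on facts that exist only after the tooth is removed. The inclusion criteria contain "Intact socket walls post-extraction", a bleeding socket and an extraction without a flap or bone removal; the exclusion criteria mirror the first two.

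Clinical procedure takes the steps in order: extraction, curettage, exclusion ("The case will be excluded if" the socket is sclerotic without fresh bleeding, or its walls are damaged), then the graft. It adds that "The assessment of the extraction socket will be done by the clinicians performing the procedures". Allocation is not mentioned there.

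Table 1 marks "Eligibility screen for patients" and an unspecified "List of other procedures" at enrolment, "Randomisation of patients" at W0 under Allocation, and the two grafts at W0 under Post-allocation. It has no row for the extraction or the socket check.

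The Abstract says "A total of 34 adult patients, who require the extraction of a single-rooted tooth, will be randomly assigned to experimental and control group". Statistical methods makes the primary analysis intention-to-treat on all randomised participants, with multiple imputation for data missing at random. The section "Criteria for discontinuing or modifying allocated interventions" lists withdrawal of consent, discontinuation of the trial and an adverse reaction.

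**The concern.** Several passages can be read as placing allocation before extraction. The Abstract randomises patients who still need the extraction. Recruitment goes straight from consent to allocation. Patients' recruitment and informed consent has eligibility assessed before a week for reflection, so that assessment cannot be the socket check.

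If a site allocated first, Clinical procedure would remove randomised patients on the judgement of an operator whom the plan does not describe as blinded. That contradicts an analysis set of all randomised participants. Imputation would have little to work with, because an ungrafted patient has neither an augmentation baseline nor a 24-week width change. If an operator who knew the arm judged borderline sockets differently by arm, the width comparison could be biased.

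Two smaller points come with it. The consent section destroys the electronic record of anyone found unsuitable. The wall-loss limit is more than 50% in Exclusion Criteria but 50% or more in Clinical procedure.

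**Working it through.** **1. Order of events.** The readable text fits both orders, so the indications have to be weighed.

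- *For allocation first:* the Abstract's description of the population, Recruitment's short account of consent and allocation, and the pre-consent eligibility assessment. None mentions the socket. The pre-consent assessment cannot be the complete eligibility check under either order.
- *For allocation after the check:* intact, bleeding sockets are eligibility criteria, so eligibility is not established until the tooth is out. Table 1 puts eligibility before randomisation, and randomisation and graft share W0. Clinical procedure excludes and only then grafts. Socket failure is not a reason for discontinuing an allocated intervention, as it should be if allocated patients could fail.

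The second reading fits at least as well. Under it, failed sockets are screen failures and the intention-to-treat set is intact.

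**2. Size if sites allocated first.** The plan gives 34 participants, 17 per group (17 × 2 = 34). It gives no socket-failure rate f; 5%, 10% and 20% are assumed.

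| f | Expected loss, 34f | P(at least one), 1 − (1 − f)^34 | P(at least one arm below 15) |
|---|---|---|---|
| 5% | 1.7 | 0.825 | 0.10 |
| 10% | 3.4 | 0.972 | 0.42 |
| 20% | 6.8 | 0.9995 | 0.90 |

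At f = 2% the chance of at least one failure is 0.497. The last column is 1 − (1 − q)², where q is the binomial chance of losing 3 or more of 17.

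**3. Precision.** With n = 17(1 − f) per arm, the standard error of the difference is √(2/n) residual SD, and the 95% half-width uses t on 2n − 3 degrees of freedom.

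- No loss: n = 17, SE 0.343, half-width 0.700.
- f = 5%: n = 16.15, SE 0.352, half-width 0.719, ratio 1.03.
- f = 20%: n = 13.6, SE 0.383, half-width 0.791, ratio 1.13.

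Imputation does not recover this loss when baseline and outcome are both absent and no other data are used. In a simulation of 3,000 trials (baseline slope 0.5 and residual SD 1, both assumed; 20 imputations), the empirical SE was 0.357 complete-case and 0.358 imputed with 2 missing, and 0.389 for both with 7 missing.

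**4. Bias.** With equal exclusion in both arms it is 0. For unequal exclusion, suppose each arm drops exactly its worst fraction p of sockets, scored as a standard normal. The mean of those left is φ(z_p)/(1 − p).

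- 15% against 5%: difference 0.166. At an assumed socket–outcome correlation of 0.3, 0.166 × 0.3 = 0.050 SD; at 0.5, 0.083 SD.
- 20% against 10%: difference 0.155, giving 0.047 and 0.078 SD.

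The matching standard errors are √(1/16.15 + 1/14.45) = 0.362 and √(1/15.3 + 1/13.6) = 0.373. The larger biases are 0.083/0.362 = 0.23 and 0.078/0.373 = 0.21 of a standard error.

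**The case for a change.** The strongest reply is that a plan should not leave the order to inference. Table 1's eligibility screen is marked only at enrolment, so it does not settle when the socket is judged, and a site could allocate on arrival. At the assumed rates at least one failed socket is likely, and at 20% an arm would probably fall below the 15 per group that Sample size cites from the literature. One sentence would close the question.

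Part of this stands: the readable text does not state the order, and a sentence would cost little. But the gap may not exist for the sites. Figure 1 is captioned as the CONSORT flowchart, where exclusions and randomisation are normally shown in sequence, and its absence here comes from text extraction. The high probabilities measure the chance of one failed socket, which is not in itself harm. The failure rates have no basis in the documents, and the restriction to single-rooted teeth, non-surgical extraction and stable periodontal health makes lower ones plausible. Sample size also goes on to cite a wider range than 15 to 20, and sets no precision or power target.

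The record-destruction point requires a rule written for the consent stage to be extended to failed sockets, which the text does not do. The wall-loss mismatch is real, and the two passages must be reconciled, but it is a clerical slip that affects only a loss of exactly 50%.

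**Conclusion.** The concern does not hold as a fault in the plan. It is a detail missing from the readable text that sites and analysts would fill sensibly: socket status belongs to eligibility, so a failed socket is a screen failure, and the 34 randomised patients all stay in the intention-to-treat set.

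Harm would need allocation before extraction. The cost would then be a confidence interval 3% to 13% wider at assumed failure rates of 5% to 20%. Bias would need, in addition, exclusion that differs by arm; under the differences and correlations assumed above it is 0.05 to 0.08 SD, under a quarter of a standard error. For a pilot meant to supply planning figures for a full trial, neither would alter the conclusions. The judgement rests on the natural reading of the eligibility criteria and Table 1; a Figure 1 that showed allocation before the socket check would reopen it.

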The primary outcome is the difference between the two low substitution rate bone substitutes, natural (Bio-Oss[®]) and synthetic (Bonalive[®]), in preserving the alveolar ridge dimensions assessed by changes in the width (expressed in millimetres) from augmentation (baseline) to 24-week post augmentation. Assessment will be done using intra-oral scanners (this does not involve radiographs) or impressions and clinical photographs.

Secondary outcomes

- Changes in height (expressed in millimetres) from augmentation (baseline) to 24-week post augmentation. Assessment will be done using the periapical radiographs taken pre-extraction and at 24-week follow-up and intra-oral scanners (this does not involve radiographs) or impressions and clinical photographs.
- Changes in the vertical crestal bone level (expressed in millimetres) assessed with periapical radiographs taken pre-extraction and 24-week post augmentation. The technique used for this assessment will be the same as that used by Solakoglu et al.(26) to evaluate changes in the alveolar bone crest in similar research.
- Presence of bone around the alveolar ridge assessed using a biopsy, histology (qualitative assessment of bone infiltration) and PCR to determine the concentration (in nanograms) of gene expression for bone markers (including osteopontin, osteocalcin) at 24-week post augmentation.

Sample size

According to Charles et al. (27) four factors are required to calculate the sample size: significance level, power, difference between groups and standard deviation. However, considering the limited availability of information in this area (only one study was identified conducted by Rignon-Bret et al.(28)

The research team, supported by the advice provided by statisticians, decided to conduct a pilot study. Even though a pilot study does not require sample size calculation using the aforementioned four factors, (29) 15 to 20 participants per group are required to ensure the scientific validity of the pilot study results (30). More recently, further information has been provided for the validity of the results of pilot RCT indicating a wider range of participants (31). Therefore, we used a pragmatic approach informed by the literature and we will recruit a total of 34 participants with 17 per group. The results of the pilot study will generate the four factors to calculate the sample size for the full-scale RCT.

Recruitment

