Recruitment will be focused on private dental clinics in the Midlands, Southeast England and Northwest England

Clinicians: Experienced Implant surgeons at centres approved by lead researchers. Approval will be based on appropriate clinical setup, clinician experience and patient volume.

Patients: Patients who meet the inclusion criteria will be invited to take part in the study. They will consent to using either of the bone substitute materials and be randomly allocated to a group.

Recruitment will start as soon as ethics approval has been granted.

The recruitment strategy will increase potential participants' awareness of the health problem being studied and its potential impact on their health.

Clinician-patient ratio

The patients will be spread across 2-4 surgeries to ensure we meet the target sample size in a few months.

Randomisation, sequence generation, allocation and blinding

The randomisation, sequence generation and allocation concealment will be performed using the sealed envelope online system (<https://www.sealedenvelope.com/>) (32) . The randomisation will be 1:1. The patient will be the unit of randomisation and intervention.

All patients receiving the bone substitutes will be blinded to the treatment in our study. However, patients will know which bone substitute they have received after their final review at 24-week follow-up.

Data collection

Clinicians will collect data at baseline and at 24-week follow-up using a paper template. Then data will be transferred into Excel and SPSS and prepared for the data analysis. All paper records, except consent forms, will be destroyed at patients' last visit. Secure and irreversible destruction processes will include shredding and disposal of records using the University's confidential waste service.

Data management

The procedure will be conducted using the data management template provided by UKRI. Data will be managed following the procedure used in previous studies (26,28). Input data will

be saved and stored on a password-protected system. Only individuals authorised by the CI will be allowed to access the data. Paper data, such as Patients' informed consent will be kept in a locked cabinet by the clinicians.

Statistical methods

The primary analysis will be the intention-to-treat (ITT), including all randomised participants in the assigned group, regardless of their adherence to the protocol or their withdrawal.

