Missing data will be assessed and treated using multiple imputations if missing at random (MAR).

To check for normality, each variable will be analysed using the Shapiro-Wilk test.

Primary outcome

The primary outcome is the difference between the two bone substitutes, natural (Bio-Oss[®]) and synthetic (Bonalive[®]), in preserving the alveolar ridge dimensions assessed by changes in the width of the alveolar ridge (expressed in millimetres) from augmentation (baseline) to 24-week post augmentation. It is expected to be a continuous variable, therefore, the comparison between groups at 24 weeks will be performed using a linear regression model (ANCOVA), including the baseline measurements as the covariates. The recent literature suggests using of ANCOVA as the statistical method of choice for the analysis of intervention effect and adjustment for baseline variables for three reasons: efficiency, precision and power (33).

Secondary outcomes

- The changes in the height of the alveolar ridge (expressed in millimetres) from grafting (baseline) to 24-week follow-up (post grafting) assessed using either intra-oral scanners or impressions and clinical photographs. It is expected to be a continuous variable; therefore, the comparison between groups at week 24 will be performed using the unpaired t-test for a normally distributed variable or the Mann-Whitney U test for non-normally distributed.
- The changes in vertical crestal bone levels between the groups (expressed in millimetres) will be compared using an unpaired t-test or Mann-Whitney U test according to the variable distribution. This will be assessed using radiographs pre-extraction and at 24-week follow-up.
- Presence of bone will be assessed using biopsy used for histology (qualitative assessment of bone infiltration) and PCR to determine the concentration (in nanograms) of gene expression of the bone markers (including osteopontin and osteocalcin).

- The comparison of the concentration of gene expression between the groups at 24-week will be performed using the unpaired t-test for a normally distributed variable or the Mann-Whitney U test for non-normally distributed

Data monitoring

This trial is designed to minimise the risk, as demonstrated in the previous trials by Rignon-Bret et al. (28) and Solakoglu et al. (26). Therefore, no formal committee has been organised, and no interim analysis of the impact of the intervention has been planned.

Risk and safety issues

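### Baseline ridge width, the ANCOVA covariate, is scheduled after allocation and is not fixed before graft placement, so the arm could influence it

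*Combined protocol and SAP*

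**What the plan says.** Four parts of the combined protocol and SAP bear on this.

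- **Timing in the text.** Clinical procedure states that "Intra-oral scans or impressions with clinical photographs will also be taken on the day the procedure is carried out". It does not give the order relative to extraction, allocation or packing. The only record tied to a time before extraction is the periapical radiograph.
- **Timing in the schedule.** In "Table 1 Schedule of enrolment, intervention and assessments", width and height are marked twice: at W0 under "Post-allocation", in the column that holds the two graft rows, and at W24. Neither has a mark under enrolment or allocation.
- **Definition of baseline.** The primary outcome is change in width "from augmentation (baseline) to 24-week post augmentation". The Abstract, Key research questions and Statistical methods likewise equate baseline with augmentation.
- **Use in the analysis.** The 24-week comparison of width "will be performed using a linear regression model (ANCOVA), including the baseline measurements as the covariates". Height has no covariate: "the comparison between groups at week 24 will be performed using the unpaired t-test for a normally distributed variable", with a Mann-Whitney alternative.

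On who measures: "Clinicians will collect data at baseline and at 24-week follow-up using a paper template". The section on randomisation and blinding describes blinding of patients only, and no blinded assessor is mentioned.

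**The concern.** Baseline adjustment in a randomised trial is safe because treatment cannot reach a value recorded before assignment. A value recorded after assignment loses that guarantee.

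There are two routes by which the arm could affect it here. First, an operator who knows the allocation takes the scan or impression. Second, if the record is made after packing, the surface contour may include the graft. The documents give some reason to think the materials could sit differently on day 0. The stated granule sizes are 0.5–0.8 mm for the test material and 0.25–1 mm for the comparator. Appendix 2 describes loose moistened granules, whereas Appendix 3 describes a block that is cut and moulded.

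Any day-0 difference arising in this way enters the estimate with the opposite sign: the arm that looks wider at the start is charged with extra loss. The Sample size section says that the pilot will supply the inputs for the full trial, including the difference between groups, so an error here would carry forward.

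**Working it through.** **The plan's own figure.** The sample size is 17 per group, and 2 × 17 = 34 agrees with the stated total. No alpha, power, effect size or SD is given, so there is no power calculation to reproduce, and this point does not dispute the number.

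**Set-up.** Let W be pre-graft width, T the arm (0 or 1), B = W + d·T the recorded baseline, and Y the 24-week width. Y has slope rho on W within arm and a true arm difference tau. Here d is the arm-related difference in recorded day-0 width.

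**What the ANCOVA estimates.** Substituting W = B − d·T gives

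Y = constant + rho·(B − d·T) + tau·T + error = constant + rho·B + (tau − rho·d)·T + error.

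The treatment coefficient is tau − rho·d, so the bias for tau is −rho·d. Using Y − B as the dependent variable with B still in the model changes the slope to rho − 1 and leaves the coefficient of T unchanged. Modelling change does not remove the problem.

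**Inputs.** From the plan: 17 per arm, 1:1, ANCOVA on baseline. Assumed, because the documents give no values: tau = 0, equal SDs at the two times (so that slope equals correlation), two-sided 5% test, d of 0, 0.25 or 0.5 SD, and rho of 0.5, 0.7 or 0.9.

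**Precision.** SE ≈ √(2/17) × √(1 − rho²) = 0.343 × √(1 − rho²) SD, which is 0.297, 0.245 and 0.150 for rho = 0.5, 0.7 and 0.9.

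**Results** (20,000 simulated trials per setting, t test on 34 − 3 = 31 degrees of freedom):

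| d (SD) | rho | Bias = −rho·d (SD) | Bias / SE (absolute) | False-positive rate |
|---|---|---|---|---|
| 0 | 0.5, 0.7, 0.9 | 0 | 0 | about 5% |
| 0.25 | 0.5 | −0.125 | 0.42 | 7% |
| 0.25 | 0.7 | −0.175 | 0.71 | 10% |
| 0.25 | 0.9 | −0.225 | 1.50 | 30% |
| 0.5 | 0.5 | −0.25 | 0.84 | 12% |
| 0.5 | 0.7 | −0.35 | 1.43 | 26% |
| 0.5 | 0.9 | −0.45 | 3.01 | 79% |

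With W as covariate in place of B, the rate was about 5% in every row.

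**A smaller shift.** With an assumed SD of 1.5 mm, a day-0 difference of 0.25 mm (0.25/1.5 = 0.17 SD) gives 6%, 7% and 16% for the three values of rho.

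**If the target is change from the grafted ridge.** That quantity is tau − d. The planned ANCOVA misses it by (tau − rho·d) − (tau − d) = (1 − rho)·d. A pre-allocation covariate estimates tau and misses it by d. At d = 0.5 SD and rho = 0.7 these errors are 0.15 and 0.50 SD. The choice of baseline and the choice of target therefore have to be made together.

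**Height.** The ANCOVA algebra does not apply. If the change in height is compared without adjustment, d enters the arm difference in full, as −d.

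**The case against.** A reader might infer that the scan is taken after packing, because the sentence follows the description of packing and sealing. The documents do not support that as fact. The same sentence also follows the two-week suture review and the advice on flying, so the section is not in time order. Allocation and the first post-allocation column are both W0, and a scan after allocation but before packing would fit the same cell. This part of the objection stands. What remains is that a post-allocation record is what the schedule states, and that nothing rules out a post-graft one.

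The size of d is also unsupported and may be near zero. Eligibility requires intact socket walls and extraction without a flap or bone removal. The material is packed without pressure, and the protocol expects the two products to support the ridge similarly. The same collagen matrix is described for both arms, so the text gives no reason to expect a matrix effect. All of this stands. It limits the likely size but does not establish d = 0, and the similarity of the products is an expectation about what the trial is testing.

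The strongest objection concerns the target. If the investigators truly mean change from the grafted ridge, a pre-allocation covariate does not answer that question, as the working shows. It would be wrong to say that moving the baseline leaves the question untouched. However, the planned ANCOVA does not recover that target either unless d = 0 or rho = 1, and Statistical methods describes a comparison between groups at 24 weeks, which supports tau as the target. The plan has to choose.

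Finally, this is a pilot with no power calculation, so false-positive rates matter less than in a confirmatory trial. That is fair, although a between-arm test is planned and the estimated difference is meant to inform the full trial.

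**Conclusion.** The point holds as a defect in when the covariate is measured. The plan schedules baseline width after allocation, leaves its order relative to packing open, has it collected by clinicians not described as blinded, and then adjusts the primary comparison for it.

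A reader might go further and conclude that the primary comparison is biased. The documents do not show that. It needs a non-zero d, and they give no value. With d = 0 there is no bias and the error rate is about 5%. Under the assumed range of 0.25 to 0.5 SD and rho of 0.5 to 0.9, bias is about −0.13 to −0.45 SD and the false-positive rate runs from 7% to about 80%. The top figure needs both the largest shift and a correlation of 0.9 across 24 weeks of remodelling, and should be read as a worst case. The influence of an operator who knows the arm follows the same algebra, but the documents offer nothing with which to size it.

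The plan should change before recruitment: the remedy is cheap, and a missing pre-graft record cannot be recreated later.

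**What to change.** 1. In Clinical procedure, state that the scan or impression used in the analysis is taken at one fixed step, the same at every site, before allocation is revealed and before the graft is placed. Say whether that step is before or after extraction, since these are different baselines.
2. Move the W0 marks for width and height in Table 1 to match.
3. In Statistical methods, name that value as the ANCOVA covariate and state the primary target as the between-arm difference in 24-week width, adjusted for pre-allocation width. Use the same baseline for height.
4. Align the wording that equates baseline with augmentation in the Abstract, Key research questions, Outcomes and Statistical methods.
5. If a post-graft scan is also wanted, report it descriptively only.

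The cost is a reordering of steps within the same visit and small changes to the definition of baseline. No extra visit is needed, and no extra procedure if the existing scan is simply moved. If the chosen step is after extraction, the allocation must be revealed after it, which the sites would need to build into their sequence. The investigators also give up change from the grafted ridge as the primary target, and should make that choice explicitly.
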